1.4. Trial Process

Visit time Visit contents	Screening/Baseline period	Treatment period	Observation period	Follow-up period	
	Preoperatively -1 d ~ 0 d	Day of operation/0 d	Postoperatively 24 h ± 12 h	Postoperatively 7 d ± 2 d	Postoperatively 90 d ± 14 d
Signing of ICF	×				
Medical history	×				
Preoperative diagnosis	×				
Vital signs ¹	×		×	×	
NIHSS score ²	×		×	×	
mRS score ³	×				×
Laboratory test ¹	×		×		
Pregnancy test ⁵	×				
Cerebral CT or MR ^{6,7}	×		×		
Cerebrovascular DSA ⁷	×				
Verification of eligibility criteria		×			
Randomization		×			
Operations		×			
Antiplatelet and anticoagulant medication	×	×	×	×	×
Adverse event		×	×	×	×
Device defect		×			

Figure1 Study Flowchart

Note:

- 1) Vital signs include heart rate and blood pressure.
- 2) NIHSS score: assessing the degree of neurological impairment of the subject.
- 3) MRS score: assessing the degree of disability of the subject.
- 4) Laboratory tests (The laboratory test results at 24 h preoperatively are accepted during the screening period, and one laboratory test within 9d postoperatively is sufficient):
- 5) Blood routine: Red blood cell, hemoglobin, white blood cell count, and platelet count
- 6) Blood chemistry: Urea nitrogen (urea), serum creatinine, blood glucose
- 7) Coagulation: Prothrombin time, activated partial thromboplastin time and INR
- 8) Only for women of childbearing potential who are planning to become pregnant, blood or urine pregnancy test

result is acceptable.

- 9) Cerebral CT or MR is performed when the onset time is ≤ 6 h; cerebral CT or MR is performed when the onset time is 6 (exclusive)-24h (inclusive) to determine whether ASPECTS score ≥ 6 is met; (if immediate CT perfusion imaging or MR perfusion imaging is feasible, CTP or MRP is recommended to assist in the assessment of the infarct core to determine whether ASPECTS score ≥ 6 is met).
 - 10) CT or MRI images and DSA images during thrombectomy are burned on a CD in DICOM format and evaluated by a central interpretation room.
 - 11) Randomization: An electronic randomization system is logged into for randomization.
- * If any of the micro-guidewire and microcatheter does not pass through the thrombus segment of the target vessel during the operation, or if the thrombectomy device is not used for thrombectomy, this subject is statistically processed as having a blank randomization number.

1.5. Sample Size

The primary endpoint of this trial is the success rate of recanalization. It adopts a prospective, multicenter, randomized controlled design, with a non-inferiority test.

Based on existing clinical evidence and expert consensus, the pre-specified non-inferiority margin was set at 12.5%, assuming both groups achieved an 89% recanalization rate within 24 hours. With a one-sided significance level α of 0.025 and a power $(1-\beta)$ of 80%, the calculated sample size per group is 99 subjects. Considering a maximum possible 10% dropout rate, the sample size per group is increased to 110 subjects, totaling 220 subjects. Based on statistical principles,

The corresponding sample size formula is:

$$n_T = n_C = \frac{(Z_{1-\alpha/2} + Z_{1-\beta})^2 [P_C(1 - P_C) + P_T(1 - P_T)]}{(|D| - \Delta)^2}$$

In the formula, n_T and n_C are the respective sample size of the test group and control group; $Z_{1-\alpha/2}$ and $Z_{1-\beta}$ are the percentiles in standard normal distribution; P_T is the expected success rate of recanalization in the test group, P_C is the expected success rate of recanalization in the control group; $|D|$ is the absolute value of the difference between groups in the expected recanalization, $|D|=|P_T-P_C|$; Δ is the non-inferiority margin (taking the negative value).

This trial will be conducted simultaneously across multiple clinical trial sites. Considering feasibility and enrollment progress, the enrollment quotas for each participating site will be adjusted based on actual circumstances to ensure balanced enrollment across centers. The final enrollment size

for any single site should not exceed 50% of the total number of cases.

2. Evaluation Endpoint

2.1. Efficacy Endpoints

2.1.1. Primary efficacy endpoint

Success rate of immediate recanalization.

Vascular recanalization success: Target vessel recanalization with mTICI grade 2b or 3.

Success rate of immediate recanalization = Number of subjects in this group with immediate recanalization success / Number of subjects in this group undergoing intracranial thrombectomy with stenting $\times 100\%$.

Vascular recanalization success is assessed independently by both the treating clinician and a central reading laboratory. In case of disagreement, the blinded assessment by the central reading laboratory prevails.

2.1.2. Secondary efficacy endpoints

1. 90-day Postoperative mRS 0-2 Score Ratio: $\text{mRS 0-2 Score Ratio} = \text{Number of subjects with mRS 0-2 score at 90 days postoperatively} / \text{Number of subjects undergoing thrombectomy via intracranial thrombectomy device} \times 100\%$.
2. Time to recanalization: $\text{Time to recanalization} = \text{End time} - \text{Femoral artery puncture time}$ (If recanalization is successful, the end time is the time of successful recanalization; if no recanalization occurs, the end time is recorded as the time of procedure completion). Here, recanalization refers to successful target vessel recanalization with mTICI grade 2b or 3 following thrombectomy using the investigational device.
3. Postoperative NIHSS score improvement >4 points: Improvement in NIHSS score at 24 ± 12 hours postoperatively, 7 ± 2 days postoperatively/prior to discharge compared to baseline. $\text{Percentage of subjects with } >4\text{-point NIHSS improvement} = \text{Number of subjects in this group}$

with >4-point postoperative NIHSS improvement / Number of subjects in this group treated with thrombectomy via thrombotic stents $\times 100\%$.

4. Success rate of device operation: Defined as successful delivery of the device to the target lesion site, followed by accurate deployment and retrieval. Success rate of device operation = Number of devices successfully delivered, deployed, and retrieved in this group / Total number of devices used in this group $\times 100\%$.

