6.1.6. Effectiveness Evaluation Methods

- 1) Description of effectiveness endpoints
 - a) Primary effectiveness endpoint: success rate of instant recanalization
 - b) Secondary effectiveness indicators: Proportion of subjects with mRS scores of 0-2 on 90d postoperatively, time from femoral artery puncture to recanalization/the end time of operation for subjects whose recanalization failed, proportion of subjects with NIHSS score decrease > 4 , and success rate of device operation
- 2) Selection of Method and Time to Evaluate, Record and Analyze Effectiveness

Indicators

Primary endpoint:

● Success rate of instant recanalization

Recording time and method: During thrombectomy, cerebral vascular DSA examination will be performed to analyze whether the recanalization success is achieved. If the recanalization is affected due to in situ atherosclerotic stenosis, vascular dissection and vasospasm after thrombectomy, the investigator can handle it in an appropriate way and determine whether the target vessel is successfully revascularized according to the recanalization after treatment.

* Recanalization success was evaluated separately by clinicians and a central interpretation room independent of the study, and when the evaluation results were inconsistent, the results of the blind evaluation by the central interpretation room prevailed.

Formula: Success rate of instant recanalization = Number of subjects with instant recanalization success in this group/Number of subjects treated with revascularization devices in this group $\times 100\%$.

Criteria for instant recanalization success: target vessel recanalization, with mTICI grade of 2b or 3. The mTICI grading is shown in Appendix 3.

Secondary endpoint:

● Proportion of mRS scores of 0-2

Recording time and method: preoperatively and 90 ± 14 d postoperatively. Postoperative subjects' degree of disability will be analyzed by 90-d mRS scores postoperatively. The mRS score is based on mRS scale (as shown in Appendix 4).

Proportion of subjects with mRS scores of 0-2 = Subjects with mRS scores of 0-2 on 90d postoperatively/Number of subjects treated with intracranial thrombectomy device $\times 100\%$.

● Time from femoral artery puncture to recanalization/the end time of operation for patients whose recanalization failed

Evaluation time: Intraoperatively

Evaluation site: target vessel

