Evaluation method: The recanalization time will be judged by intraoperative procedure and the vascular condition shown by imaging.

Formula: Recanalization time = Recanalization success time - Femoral artery puncture time

Precautions: The recanalization time is the time from the completion of femoral

artery puncture to recanalization success. If the vessel is not revascularized, the end time point is recorded as the time point at the end of operation. Criterion for instant recanalization success: target vessel recanalization with mTICI grade of 2b or 3 after thrombectomy with the investigational device. The investigator's judgment intraoperatively shall prevail.

- **Proportion of subjects with NIHSS score decrease > 4**

Recording time and method: The preoperative and postoperative NIHSS scores are compared by three time points: pre-operation, 24 ± 12 h postoperatively and 7 ± 2 d postoperatively (before discharge in case of premature discharge) to analyze the degree of impairment and improvement of neurological functions preoperatively and postoperatively. The NIHSS score is the total score based on NIHSS scale (as shown in Appendix 5).

Proportion of subjects with NIHSS score decrease > 4 = Number of subjects with NIHSS score decrease > 4 postoperatively in this group/Number of subjects treated with thrombectomy through stents in this group $\times 100\%$.

- **Success rate of device operation**

Definition: The success rate of device operation is the proportion of device operation success. Device operation success is defined as successful delivery of the investigational device to the diseased vessel site to complete accurate deployment and withdrawal.

Evaluation time: Intraoperatively (evaluation endpoint)

Evaluation site: target vessel

Evaluation method: The success rate of device operation is calculated by intraoperative evaluation of whether the delivery, deployment and withdrawal of the thrombectomy device are completed.

Formula: Device operation success = Number of devices delivered, deployed and withdrawn/Number of all investigational devices used in this group $\times 100\%$.

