6.2.1.2. Randomization

Randomization will be performed via an electronic randomization system after screening for inclusion and exclusion criteria. The investigator will log into the randomization system, fill in the subject information and then submit, and the system will automatically give the randomization results. The investigator should select the corresponding test product to treat the subject according to the results given by the electronic randomization system. In Group A, Sinomed Neurovita Ghunter Revascularization Device will be used, and in Group B, Covidien Solitaire FR will be used. Once the subject information is entered into the electronic randomization system, no deletion will be allowed, and all operations will be automatically left on the system for verification.

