6.2.1.3. Visit Schedule

1) Visit 1: Screening/baseline period (-1 d ~ 0 d)

After all the subjects (or their guardians) sign the ICF, the investigator will screen the subjects according to the inclusion/exclusion criteria of the study. During this period, the following visit contents need to be completed:

- i. Signing of ICF;
- ii. Recording of basic information of the subject;
- iii. Present medical history: onset time and admission time;
- iv. Medical history: history of allergy, history of stroke, history of other significant diseases (e.g., presumed septic emboli or suspected bacterial endocarditis), history of neurological diseases;
- v. Vital signs (blood pressure, heart rate);
- vi. NIHSS score;
- vii. MRS score, ASPECTS score (required within 6 - 24 h of onset);

Laboratory examination:

- viii. Pregnancy testing (Only for women of childbearing potential who are planning to become pregnant)
- ix. Administration of anticoagulant and antiplatelet drugs;
- x. Cerebral CT or MR will be performed, and the following information will be recorded:
 - a) When the onset time is ≤ 6 h, cerebral CT or MR is performed;
 - b) Cerebral CT or MR is performed when the onset time is 6 (exclusive)-24h (inclusive) to determine whether ASPECTS score ≥ 6 is met; (if immediate CT perfusion imaging or MR perfusion imaging is feasible, CTP or MRP is recommended to assist in the assessment of the infarct

core to determine whether ASPECTS score ≥ 6 is met).

* For laboratory tests and imaging tests, the results after this admission and the results of external hospital examinations within 24h preoperatively are acceptable.

c) Other significant abnormal conditions.

2) Visit 2 (0 d):

i. Recording of cerebral vascular DSA:

- a) Name of target vessel and lesion segment, proximal diameter of occluded vessel
- b) mTICI image grading postoperatively
- c) Does the patient suffer from carotid origin occlusion or carotid dissection or arteritis?
- d) Is the vessel access so tortuous that makes it difficult for the investigational/control device to reach the target location?

ii. Recording of the operations:

- a) Date of operation, femoral artery puncture time, operation start and recanalization time (or end time)
- b) Intraoperative treatment method (Are implant stent, balloon dilatation and antithrombotic drugs used)

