6.6.3. Secondary efficacy endpoint

Table29 mRS 0-2 at 90 days post-surgery

Item	Indicator	FAS		PPS	
		Experimental Group	Control Group	Experimental Group	Control Group
mRS 0-2 at 90 days post-surgery	Yes n(%)				
	No n(%)				
	Total (Missing)				
	Statistic (CMH)				
	P-value				
90-day postoperative mRS	Grade 0 n(%)				
	Grade 1 n(%)				
	Grade 2 n(%)				
	Grade 3 n(%)				

Item	Indicator	FAS		PPS	
		Experimental Group	Control Group	Experimental Group	Control Group
	Grade 4 n(%)				
	Level 5 n(%)				
	Level 6 n(%)				
	Total (Missing)				
	Statistic				
	P-value				

Table30 Recanalization Time

Item	Indicator	FAS		PPS	
		Experimental Group	Control Group	Experimental Group	Control Group
Recanalization Time (min)	N(Missing)				
	Mean(SD)				
	Median				
	Q1, Q3				
	Min, Max				
	Statistic				
	P-value				

Note: Time to reperfusion = End time - Femoral artery puncture time (If reperfusion is successful, the end time is the time of successful reperfusion; if reperfusion fails, the end time is recorded as the time of surgical completion).

Table31 Postoperative NIHSS Score Improvement

Item	Indicator	FAS		PPS	
		Experimental Group	Control Group	Experimental Group	Control Group
Preoperative NIHSS Score	N(Missing)				
	Mean(SD)				
	Median				
	Q1, Q3				
	Min,Max				
	Statistic				
	P-value				
NIHSS score at 24±12 hours postoperatively	N(Missing)				
	Mean(SD)				
	Median				
	Q1, Q3				
	Min,Max				
	Statistic				
	P-value				

Item	Indicator	FAS		PPS	
		Experimental Group	Control Group	Experimental Group	Control Group
NIHSS score reduction >4 points (postoperative 24±12 h vs. preoperative)	Yes n(%)				
	No n(%)				
	Total (Missing)				
	Statistic				
NIHSS score at 7±2 days post-op/prior to discharge	P-value				
	N(Missing)				
	Mean (SD)				
	Median				
	Q1, Q3				
	Min,Max				
	Statistic				
Proportion of subjects with NIHSS score reduction >4 points (7 ± 2 days post-op/prior to discharge)	P-value				
	Yes n(%)				
	No n(%)				
	Total (Missing)				
	Statistic				
	P-value				

Table32 Device Operation Success Rate (per device unit)

Item	Indicator	FAS	PPS
Whether Device Operation Was Successful	Yes n(%)		
	No n(%)		
	Total (Missing)		

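### For recanalisation time the Protocol lets the unblinded operator decide success and the SAP names no reader, while the primary endpoint uses the blinded core-lab read of the same mTICI criterion

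*SAP*

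**What the plan says.** **Primary endpoint.** Clinician and core laboratory both grade the target vessel, and success is mTICI 2b or 3. Protocol 6.1.6 says that "when the evaluation results were inconsistent, the results of the blind evaluation by the central interpretation room prevailed". SAP 2.1.1 has the same rule: "In case of disagreement, the blinded assessment by the central reading laboratory prevails". Table 23 (SAP 6.6.1) is the core-laboratory table.

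**Time endpoint.** Further on in Protocol 6.1.6, the entry for puncture-to-recanalisation time restates the mTICI 2b/3 criterion and adds: "The investigator's judgment intraoperatively shall prevail". SAP 2.1.2 item 2 gives its own definition: "Here, recanalization refers to successful target vessel recanalization with mTICI grade 2b or 3 following thrombectomy using the investigational device". It names no reader. Neither does the Table 30 note in SAP 6.6.3.

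**Failures.** Subjects without recanalisation also get a time. SAP 2.1.2: "if no recanalization occurs, the end time is recorded as the time of procedure completion". Table 30 note: "if reperfusion fails, the end time is recorded as the time of surgical completion".

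**Who knows the arm.** Protocol 6.2.1.2: "The investigator should select the corresponding test product to treat the subject according to the results given by the electronic randomization system". The operator is therefore unblinded.

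**What is recorded.** Visit 2 in Protocol 6.2.1.3 lists "operation start and recanalization time (or end time").

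Protocol 3.2 and SAP 1.3 both list this time among the outcomes tested between devices, and Table 30 has a row for a P-value.

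**The concern.** The plan uses a blinded read to decide recanalisation for its main result. For the time endpoint, an unblinded person decides both whether the event happened and when the clock stopped.

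Take a subject graded 2b by the operator and 2a by the core laboratory. Table 23 counts a failure. Under the Protocol, Table 30 uses the operator's success stamp. If the SAP 2.1.1 rule were carried over to SAP 2.1.2, the subject would be treated as not recanalised and timed to the end of the procedure. Because the SAP names no reader, a programmer working from it alone could defend either value.

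If operators over-call success more often with one device than with the other, some of that arm's failures enter the comparison as shorter times. The device then looks faster for a reason unrelated to speed.

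**Working it through.** **1. The plan's own figure.** With 89% in both arms, a 12.5-point margin, one-sided 0.025 and 80% power (SAP 1.5):

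n = (1.960 + 0.842)² × 2 × 0.89 × 0.11 / 0.125² = 98.36, so 99 per arm; 99 / 0.9 = 110.

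This reproduces, and nothing below affects it.

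**2. How many subjects could be involved.** Expected core-lab failures per arm: 110 × 0.11 = 12.1, about 12. If the operator called half of these 2b/3 (an assumption), about 6 per arm would be timed to an operator stamp. The documents give no disagreement rate.

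**3. Shift in mean time.** Let d be the share of subjects called success by the operator and failure by the core laboratory. Let g be the minutes from the operator's stamp to procedure end. The arm mean moves by d × g.
- Lowest case: 0.02 × 5 = 0.1 min. Highest case: 0.10 × 30 = 3.0 min.
- Between-arm bias with equal d and g: 0.
- With d of 10% versus 2%: 0.08 × 5 = 0.4 min to 0.08 × 30 = 2.4 min.

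**4. Type I error of the rank-sum test.** The simulation has 110 per arm and no true device difference. Assumed inputs are 11% core-lab failures, log-normal success times (median 60 min, log-SD 0.5), recognised failures running 40 min longer, and over-called failures stopping at the operator's time. The test is two-sided at 0.05. Ranges come from two separate sets of 4,000 runs; the 60/40 row is from 3,000 runs.

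| Share of failures over-called, arm 1 / arm 2 | Operator decides |
|---|---|
| 0% / 0% | 4.7–4.8% |
| 50% / 50% | 5.0–5.2% |
| 60% / 40% | 5.2% |
| 75% / 25% | 6.8–7.3% |
| 100% / 0% | 14.2–14.8% |

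With core-lab status and all failures ranked last, the error was 4.5% to 5.2% at 0/0, 50/50, 75/25 and 100/0. The simulation standard error near 5% is √(0.05 × 0.95 / 4,000) = 0.34 points. If recognised failures run only 20 min longer, the operator-based error falls to 5.6% (75/25) and 8.0% (100/0).

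**5. Is changing the reader enough?** Keep the plan's procedure-end rule, use core-lab status, and take the 100/0 case (3,000 runs). With procedure end 5, 10 or 20 min after the operator's stamp, the error is 12.0%, 9.7% or 6.4%, against 14.4% when the operator decides. An operator who believes the vessel is open probably stops soon after (an assumption), so procedure end may lie close to the stamp. Changing the reader then removes only part of the bias. Ranking failures last removes it.

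**The case against.** The Protocol rule is explicit and pre-specified. It sits under the time endpoint, and the core-lab rule sits under the primary endpoint. A reader might infer that the two contradict each other. They do not, because two endpoints may have different adjudicators. This stands, and the defect in the SAP is silence about the reader.

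A recanalisation time also has to be read during the procedure. That stands too, but it justifies the operator's clock reading. It does not justify letting the operator decide success when a blinded read is available.

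A reader might think it wrong that a Table 23 failure has a time in Table 30 at all. The documents do not support this, since every failure gets a time by design. The only question is how the discordant subject is classed and which end point is used.

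A reader might also infer that Table 30 cannot be interpreted beside the primary result. That goes too far. SAP 6.6.2 (Tables 26 to 28) repeats the primary analysis on EDC data with mTICI by arm, so a net difference in over-calling would be visible there. Those tables do not count the discordant subjects, however, and they do not correct Table 30.

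Finally, every quantity behind the type I error is assumed, and real inflation needs strongly unequal over-calling. This stands and limits the weight of the point.

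**Conclusion.** The point holds as a minor one. The Protocol gives the unblinded operator the decision on success for a between-device comparison, although a blinded read of the same threshold exists, and the SAP does not say which read applies.

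With equal or mildly unequal over-calling there is no material inflation of the type I error. It is about 7% at 75% versus 25%, and about 14 to 15% at 100% versus 0%. Over-call shares, time distribution and failure delay are all assumptions, and a shorter delay gives less inflation. Nothing in the documents shows that over-calling will differ by arm, so they do not support a claim that the comparison is in fact biased.

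Nor does the point reach the trial's conclusion. The pass/fail rule in Protocol 8.2 rests on the recanalisation rate and device-related safety, and does not use the time endpoint.

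**What to change.** In SAP 2.1.2 item 2 and in the Table 30 note:
- Take recanalisation status from the core-lab read used for the primary endpoint.
- Use the operator's clock time only where the core laboratory confirms mTICI 2b or 3.
- Rank all core-lab failures last, tied, in a two-sample rank-sum test. Name the test, because SAP 5.1 speaks of signed-rank tests while Protocol 7.1.2.1 gives the rank-sum test.
- State how a missing core-lab read is handled, since SAP section 4 imputes failure for the primary endpoint only.

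Ranking last also avoids a data problem. Visit 2 words the two times as alternatives, so procedure end may not be held for subjects the operator called successes.

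In Protocol 6.1.6, limit the investigator's judgment to the clock reading. Keep the operator-based version as a labelled sensitivity analysis, and report operator/core-lab disagreement counts by arm. If the sponsor prefers to keep the Protocol rule, the SAP should say so and add the core-lab version as the sensitivity analysis.

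The cost is SAP wording, a small Protocol wording change, and a merge of the core-lab grade with the recorded time. No new reads are needed. Slightly fewer subjects will count as recanalised, and the operator's clock may differ by minutes from the angiographic run that the core laboratory graded.
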